7.3 LOST TO FOLLOW-UP

A participant will be considered lost to follow-up if the study staff is unable to verify vital status after the subject has been discharged from the hospital. Before a participant is deemed lost to follow-up, the site investigator or designee will make every effort to regain contact with the participant or surrogate (where possible, 3 telephone calls and, if necessary, a certified letter to the participant's last known mailing address or local equivalent methods). These contact attempts should be documented in the participant's medical record or study file.

We will verify duration of survival for participants lost to follow-up or noted to have died using the Centers for Disease Control and Prevention's National Death Index (National Death Index, 2000). The subject's social security number (SSN) will be used for an exact NDI match. Contact information will be collected for the subject and alternative contact information will be collected on up to 3 individuals. Contact information and the subject's SSN will be collected on paper at the time of consent. Contact information and SSN will be maintained on paper locally and will not appear in the study database.

8 STUDY ASSESSMENTS AND PROCEDURES

8.1 DESCRIPTION OF STUDY PROCEDURES

All clinical study procedures will be performed in accordance with Good Clinical Practice (GCP) standards. Study assessments described below will be done according to the **Schedule of Activities** in **Section 1.3**.

APACHE II Score: The APACHE II consists of 12 physiological variables, age, and underlying health. The score will be calculated based on the worst values in the 24 hours prior to randomization. Calculation variables are described in **Appendix B1**.

Blood gas analysis: The following values will be recorded from the arterial blood gas (ABG) results: pH, PCO₂, PO₂, and base excess or deficit. ABG is required for baseline assessment. If no ABG is available on subsequent days, record blood gas analysis results from the venous blood gas (VBG).

Calibration of IL GEM Premier Co-oximeter and COventDS: Calibration will be performed according to device manuals and SOP. Documentation of calibration will be kept in study files.

Central Venous Pressure (CVP): CVP will be recorded if available.

Calculate Deadspace (Vd/Vt): Dead space fraction will be measured daily by the administering RT or physician prior to study drug administration using a NICO or NM3 monitor (Respironics) and the PCO₂ obtained from an arterial or venous blood gas.

Chest X-ray (CXR): The baseline frontal CXR will be reviewed by two study physician investigators to determine study eligibility. Study physician investigators blinded to treatment allocation will review and perform the assessment for the Lung Injury Score (LIS). All 4 lung quadrants will be assessed for infiltrates and pneumothoraces. If the subject is extubated on days 1-5, the study team will order a chest X-ray the

day following extubation, if not ordered by the clinical team. Chest X-rays will also be ordered by the study team for endpoint analysis on Day 7, if not ordered by the clinical team.

Clinical Laboratory Assessments: Clinical labs will be processed at each site's local laboratory and reviewed by a study investigator. If labs are required according to the **Schedule of Activities (Section 1.3)** and are not available as part of standard of care testing, they will be drawn for research. A urine or serum pregnancy test will be done for women of childbearing potential. A subject with a positive pregnancy result will not be eligible for randomization.

Concomitant Medications Review: The following medications will be recorded in the study eCRFs: aspirin, COX-2 inhibitors, NSAIDs, ACE inhibitors, steroids, phosphodiesterase inhibitors, neuromuscular blockade, inhaled NO or prostaglandins, antibiotics, diuretics. TPN use will also be recorded.

EKG: A 12 lead EKG will be obtained and reviewed daily by the study staff physician prior to study drug administration to evaluate for cardiac exclusion criteria (acute MI, ACS, or unstable atrial or ventricular arrhythmia). The study drug will not be started until the EKG is obtained and reviewed by the study physician investigator for a potential study hold. The EKG will also be officially read locally at each site.

Fluid Intake/Output: Fluid intake and output (most recent 24 hour value) or mean hourly value for most recently available period. Diuretic administration will also be recorded if applicable.

Glasgow Coma Scale (GCS): The GCS is a determination of the best eye opening, motor, and verbal responses at any given time. The GCS is documented by the clinical team as part of routine ICU nursing assessment. If not available, the GCS will be assessed by the study staff as described in **Appendix B2**.

Lung Injury Score (LIS): The lung injury score will be calculated based on the chest x-ray assessment, PaO₂, FiO₂, PEEP, and ventilator compliance measurement as described in **Appendix B3**.

Microbiological Results: Microbiological results will be recorded in the eCRF when ordered for clinical purposes.

- a) Blood cultures
- b) Urine cultures
- c) Sputum cultures
- d) BAL cultures
- e) CSF cultures if available
- f) Stool
- g) Other

Neurocognitive Testing: Neurocognitive testing will be performed via telephone interviews using the Montreal Cognitive Assessment (MoCA)-BLIND and Hayling sentence completion test as (**Appendix C**).

Oxygenation Index (OI): The OI will be calculated based on the PaO₂, FiO₂, and mean airway pressure obtained from the ventilator parameters.

Renal replacement therapy status: Renal replacement therapy status within the last 24 hours will be recorded.

Richmond Agitation Scale (RASS): RASS is a scale used to measure the agitation or sedation level of a patient. RASS scoring is documented by the clinical team as part of routine ICU nursing assessment. If not available, the RASS will be assessed by the study staff as described in **Appendix B4**.

ScvO2: ScvO₂ will be recorded if available.

Sequential Organ Failure Assessment (SOFA): The SOFA score will be calculated based on the worst values recorded in the past 24 hours. Calculation variables are described in **Appendix B5**.

- a) Worst PaO₂/FiO₂ for that date
- b) Worst creatinine (or urine output), bilirubin, and platelet count for that date
- c) Worst Glasgow Coma Scale for that date
- d) Vasopressor use and maximal dose for that date

Vasopressors and Inotropes Review: The following vasopressors/inotropes will be recorded in the study eCRFs (epinephrine, norepinephrine, phenylephrine, vasopressin, dopamine, dobutamine, phosphodiesterase inhibitors, including dose).

Ventilator Parameters: The study staff will record ventilator parameters prior to starting study drug administration. The following settings will be recorded:

- a) Mode of ventilation
- b) FiO₂ and PEEP
- c) Tidal volume, Respiratory rate (set rate and total rate), Minute ventilation, Inspiratory flow rate
- d) Peak pressure, Plateau pressure, Compliance, and Mean airway pressure. If on a pressure-cycling mode, peak pressure during inspiration will be assumed to be the plateau pressure.
- e) Pressure during inspiration if on a pressure targeted mode (PSV, PCV, etc)

Vital Signs: Heart rate (beats/min), systemic systolic, diastolic, mean arterial blood pressure (mm Hg), and body temperature (°C), will be recorded in the eCRF.

Vital Status: Vital status will be assessed at Days 28, 60, 3 months, and 6 months. Subjects who have been discharged from the hospital will be contacted by phone. Additional information will be collected on discharge status, ventilator status, and vasopressor status at Days 28 and 60.

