different from ARDS and diffuse alveolar damage. Patients with acute MI within 90 days, recent CABG, and angina pectoris are excluded because of a potential excess risk of reducing oxygen delivery to the myocardium. Patients with NYHA class IV cardiopulmonary disease are excluded because of concerns about ventricular arrhythmias and high mortality. Patients ventilated with high frequency oscillatory ventilation are excluded because administration of iCO with this mode of ventilation may be potentially unreliable. Patients on ECMO are also excluded because the effects of CO uptake and elimination from the blood during ECMO are unknown. Patients on concurrent inhaled pulmonary vasodilator therapy are excluded as these inhaled medications may interfere with the dosing of iCO.

Patients who are cigarette smokers, but otherwise eligible for inclusion, will not be excluded from potential enrollment in the study. Rather, enrolled subjects will be screened with daily COHb levels and study drug treatment held if COHb $\geq 3\%$. This criterion was implemented for our Phase Ia study and will be used in this trial as smoking history obtained from surrogate decision makers may be unreliable and the average COHb half life is 240 minutes when breathing room air and less on supplemental oxygen¹³⁴⁻¹³⁶.

Exclusion on the basis of smoking history would preclude many patients from receiving this potentially beneficial treatment. Instead, this protocol incorporates treatment holds on the basis of daily COHb levels, which will allow otherwise eligible patients to be treated safely and have the opportunity to benefit from this potentially new promising therapy. We anticipate enrolling smokers at a frequency similar to their proportion in our target populations.

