8.4 BASELINE ASSESSMENTS

The following baseline previous medical history and admission information will be recorded after informed consent has been obtained and within the 24-hour interval preceding initiation of study drug treatment.

1. Demographic and Admission Data
2. Pertinent Medical History and Physical Examination
3. Height; gender, measured body weight (MBW); calculated predicted body weight (PBW).
4. Time on ventilator prior to enrollment
5. Type of Admission
 - a. Medical
 - b. Surgical scheduled
 - c. Surgical unscheduled
 - d. Trauma
6. Presumed site of infection
7. Acute or Chronic renal failure and use of dialysis
8. Presence of the following chronic diseases:
 - a. Cancer
 - b. Hematological malignancy
 - c. AIDS
 - d. Diabetes mellitus
 - e. COPD
 - f. Asthma
 - g. Liver cirrhosis
 - h. Hypertension
 - i. Coronary artery disease
 - j. Congestive heart failure

- k. Peripheral vascular disease
- l. Dementia
- m. Prior stroke with sequelae

9. Survey of smoking history including:

- a. Ever smoker (> 100 cigarettes in lifetime)?
- b. If yes, current smoker?
 - Estimate of pack years (# packs per day) x (# years smoked)
- c. If former smoker, when did the subject quit smoking?

10. Pregnancy test (serum or urine) for women of childbearing potential

The following baseline clinical parameters will also be recorded. If more than one value is available for this 24-hour period, the appropriate values for the APACHE II calculator will be recorded. If no values are available from the 24 hours prior to study drug administration, then values must be measured prior to initiation of study drug. A full description of the below data collection is in **Section 8.1**.

Baseline Clinical Parameters

- 1. Vital Signs
- 2. CVP if available
- 3. Electrocardiogram (EKG)
- 4. Ventilator Parameters
- 5. Frontal Chest Radiograph (qualifying radiograph)
- 6. Lung Injury Score (LIS)
- 7. APACHE II Score
- 8. SOFA Score
- 9. Glasgow Coma Score (GCS)
- 10. Richmond Agitation Sedation Scale (RASS)
- 11. ABG (qualifying arterial blood gas)
- 12. SpO₂
- 13. ScvO₂ if available
- 14. Complete blood count (CBC)
- 15. Basic metabolic panel
- 16. PT/PTT/INR if available
- 17. Serum CK, AST, ALT, Albumin, Total Protein if available
- 18. Bilirubin
- 19. Lactate
- 20. Vasopressors and Inotropes Review
- 21. Fluid intake, fluid output (most recent 24 hour value) or mean hourly value for most recently available period
- 22. Renal replacement therapy status

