9.4 STATISTICAL ANALYSES

9.4.1 GENERAL APPROACH

We will use the Mann-Whitney U or t-test, chi-square (χ^2) or Fisher's exact tests to analyze baseline demographics and clinical characteristics between the treatment groups. Distribution of numerical outcomes will be evaluated prior to any analysis. Numerical outcomes will be compared between treatment arms using the Mann-Whitney U or t-test and categorical outcomes compared using either χ^2 or Fisher's exact test.

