9.4.3 ANALYSIS OF THE SECONDARY ENDPOINT(S)

We also hypothesize that iCO will reduce the severity of ARDS as measured by lung injury score (LIS), $\text{PaO}_2/\text{FiO}_2$, oxygenation index (OI), and dead space fraction (Vd/Vt). These endpoints will be analyzed using repeated measures analysis of covariance (ANCOVA) to assess the effects of treatment, time, and the interaction between time and treatment, while incorporating between-patient variation in baseline measurements and important covariates including smoking, age, sex, and severity of ARDS. Age and sex will be considered as important biological variables in all analyses.

Interaction contrasts will include polynomial trends across time, focusing on a linear trend suggesting improvement and a quadratic trend suggesting that improvement is leveling off. As part of our analysis, we will also include the interaction between treatment and entry criteria (ARDS/Sepsis vs. Non-ARDS/Sepsis Pneumonia vs. Non-ARDS/non-Sepsis Pneumonia) in the model. Because the study is not powered for the interaction between treatment and entry criteria, that test will be exploratory. We will also perform post-hoc analyses within each criteria group to generate hypotheses for future study.

With 24 subjects in the CO group and 12 subjects in the placebo arm, we will have 80% power ($\alpha=0.05$) to detect a 0.95 difference in LIS between treatment arms, assuming a conservative SD of 0.8 (**Table 7**). We will also have 80% power to detect a 78.6 mm Hg difference in $\text{PaO}_2/\text{FiO}_2$, a 12.0 difference in OI, and a 0.14 difference in Vd/Vt between treatment arms, assuming SDs of 66, 10.1, and 0.12 respectively.

Table 7. Minimal detectable difference at 80% power.

| Endpoint | SD | Detectable Difference ($\alpha= 0.05$) |
|-----------------------------|-----|--|
| LIS | 0.8 | 0.95 |
| $\text{PaO}_2/\text{FiO}_2$ | 66 | 78.6 |

| Endpoint | SD | Detectable Difference ($\alpha= 0.05$) |
|----------|------|---|
| OI | 10.1 | 12.0 |
| Vd/Vt | 0.12 | 0.14 |

Ventilator-free days (VFDs), hospital- and ICU-free days, and Sequential Organ Failure Assessment (SOFA) scores will each be analyzed separately using ANCOVA with treatment arm as the main effect. Given our modest sample size, we will only be powered to see large changes.

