Results from the Hayling Sentence Completion Test and Montreal Cognitive Assessment (MoCA) testing will be compared between CO and placebo groups using the Mann-Whitney U test or t-test (if normally distributed). If significantly different between the groups, scores from the Hayling Sentence Completion Test and MoCA testing may be incorporated into exploratory multiple regression analyses.

Mortality will be analyzed using Cox regression models for time-to-death with treatment arm as the main predictor, and with important covariates including smoking, age, and sex in the model. Hazard ratio (HR) and 95% CI for CO relative to placebo will be reported, along with Kaplan-Meier plots and estimated proportions surviving at 28, 60, and 180 days.

To address potential bias from unobserved study outcomes due to missed visits, premature withdrawal, or death and to ensure robust data analyses, we will work closely with [name] at Johns Hopkins University, who has extensive expertise with long-term outcomes assessment after acute respiratory failure and critical illness. [name] will provide his expertise and assist with statistical methods developed by his Outcomes After Critical Illness and Surgery (OACIS) Group to address missing data and assess long-term outcomes that may be “truncated due to death”. We will use the statistical software application developed by his group using R and Shiny to impute missing data among survivors given the high mortality in ARDS. We will also employ other statistical approaches used by his OACIS Group to assess long-term outcomes in critically ill patients. These include a composite endpoint approach using both functional outcome and survival, as well as other statistical methods (e.g. survivors only analyses and survivor average causal effect [SACE]).

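### APACHE II and baseline SOFA are collected but named in no outcome model; the free-day and SOFA ANCOVAs in 9.4.3 should pre-specify one baseline severity covariate each

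*Combined protocol and SAP*

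**What the plan says.** - **Collection.** The schedule of activities (1.3) requires APACHE II and SOFA at baseline. Section 8.1 defines APACHE II from 12 physiological variables, age and underlying health, and fixes its window: "The score will be calculated based on the worst values in the 24 hours prior to randomization". Section 8.4 lists it among the baseline clinical parameters ("7. APACHE II Score").
- **A second window.** Section 8.4 records baseline data over the 24 hours before study drug starts. Where several values exist, "the appropriate values for the APACHE II calculator will be recorded". It refers the reader to 8.1 for the full description.
- **Baseline comparison.** Section 9.4.1 plans tests "to analyze baseline demographics and clinical characteristics between the treatment groups". It names no individual variable.
- **Free days and SOFA.** Under 9.4.3 these outcomes "will each be analyzed separately using ANCOVA with treatment arm as the main effect". No covariate is attached. A separate sentence there asks that age and sex be considered in every analysis.
- **Other physiological endpoints.** The repeated-measures ANCOVA in 9.4.3 for LIS, PaO2/FiO2, OI and Vd/Vt takes account of baseline values, smoking, age, sex and severity of ARDS.
- **Mortality.** The Cox model is specified "with treatment arm as the main predictor, and with important covariates including smoking, age, and sex in the model". On smoking, the reasons given under 5.2 note that "smoking history obtained from surrogate decision makers may be unreliable".
- **Allocation.** 24 iCO and 12 placebo, with no stratification (6.3, 8.3.1).

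**The concern.** An ANCOVA with no named covariate is incompletely specified. The plan accepts the principle of adjusting for baseline value and severity for four endpoints, then does not carry it to free days and SOFA, although the data are already collected for both.

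Nothing in the design balances severity. Eligibility runs from sepsis-induced ARDS to ventilated pneumonia with a SOFA rise below 2 (5.1), which plausibly widens the spread in severity. Severity of ARDS, the covariate used for the other endpoints, does not clearly apply to patients without ARDS. With 12 placebo patients, a chance difference in severity can move an unadjusted estimate in either direction, and precision that is available at almost no cost goes unused.

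**Working it through.** **1. The plan's own figure.** The plan gives no power figure for free days, SOFA or mortality. The nearest is Table 7: a detectable LIS difference of 0.95 with SD 0.8, that is 0.95/0.8 = 1.19 SD, at 80% power with 24 versus 12. A two-sided 5% t-test (sidedness is not stated, so two-sided is assumed) gives 1.02 SD, or 1.02 × 0.8 = 0.82, and 90% power at 0.95. Table 7 is therefore not reproduced from its printed inputs. That is a separate matter. Below, 1.02 SD serves only as the effect that has 80% power without adjustment.

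**2. Chance imbalance.** SE of a standardised baseline difference = √(1/24 + 1/12) = 0.354. P(|difference| ≥ 0.5 SD) = 2 × [1 − Φ(0.5/0.354)] = 16%. For 0.25 SD it is 48%. With 18 versus 18, the 0.5 SD figure would be 13%.

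**3. Effect of a 0.5 SD imbalance on an unadjusted estimate.** Let r be the correlation between severity and outcome. The documents give none, so 0.2 to 0.5 is assumed. The shift is r × 0.5 SD. Given that imbalance, and with no treatment effect, the test statistic has mean r × 0.5/0.354 and variance 1 − r². The probability that it exceeds 1.96 in absolute value is the conditional type I error.

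**4. Gain from one covariate.** The SE becomes 0.354 × √(1 − r²) × √(1 + 1/32), where the last factor is the cost of estimating one random covariate; residual df fall from 34 to 33. Power comes from the noncentral t.

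| Assumed r | Shift at 0.5 SD imbalance | Conditional type I error | Power at 1.02 SD (80% unadjusted) | Detectable difference (1.02 SD unadjusted) |
|---|---|---|---|---|
| 0.2 | 0.10 SD | 5.5% | 80% | 1.02 SD |
| 0.3 | 0.15 SD | 6.0% | 82% | 0.99 SD |
| 0.4 | 0.20 SD | 6.7% | 85% | 0.95 SD |
| 0.5 | 0.25 SD | 7.5% | 89% | 0.90 SD |

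The comparator is a model with treatment alone. Age and sex are to be considered in all analyses and age is a component of APACHE II, so the true increment is smaller and the power column is an upper bound. A normal linear model is also only a rough guide to free-day outcomes.

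For SOFA adjusted for its own baseline, an assumed r of 0.6 to 0.7 would give 93–97% by the same formula. No such correlation is documented, and one value need not hold from day 1 to day 28.

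**5. Mortality.** Assume 20–50% of 36 die: 7.2 to 18 deaths.

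- Treatment plus smoking, age and sex is four parameters: 1.8 to 4.5 deaths each.
- Adding severity makes five: 1.4 to 3.6.
- Treatment plus APACHE II alone is two: 3.6 to 9.

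A Cox simulation (2,500 trials per scenario; severity log hazard ratio per SD of 0.3, 0.6 and 0.9) compared the four-term model with the same model plus severity. At a true hazard ratio of 0.3, power was 32, 33 and 35% without severity and 32, 35 and 37% with it. Unrounded, the change is −0.4 to +2.4 points. At a hazard ratio of 1, type I error was 4.3, 4.7 and 5.2% without and 4.7, 5.2 and 6.6% with. Adding severity therefore brings essentially nothing.

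**6. The two windows.** Section 8.3.1 asks for the first dose within 24 hours of randomisation. On that schedule, a window covering the 24 hours before the first dose starts at or before randomisation. It falls wholly afterwards only if the first dose is held or late.

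**The case against.** The strongest reply is that silence is not exclusion. An ANCOVA implies covariates, the Cox list is open-ended, and age and sex are to be considered everywhere. Section 6.1.4 also refers to a detail in a Statistical Analysis Plan that Section 9 does not contain, so a fuller plan may exist. This stands in part: severity is unspecified rather than ruled out. But an open list leaves the choice of covariates to be made after the data are seen, and nothing in the available text names severity for these outcomes.

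A reader might go further than the documents allow in four ways:

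- **That APACHE II enters no analysis at all.** It would plausibly appear in the baseline comparison of 9.4.1, where an imbalance could be seen. That comparison adjusts nothing, however.
- **That the results will be biased.** Randomisation keeps the unconditional type I error. What is lost is precision, and protection once a particular imbalance has occurred.
- **That mortality loses power.** Step 5 shows almost no change.
- **That the 8.4 window makes APACHE II a post-randomisation score.** On schedule it does not, and 8.4 defers to 8.1. Patients with no study procedures or treatment are left out of the analysis under 1.4, so an undefined window for never-dosed patients matters little.

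These are also secondary endpoints in a safety trial that says of the free-day and SOFA analyses that only large changes could be detected. That limits how much weight the point carries, but it does not argue against a better model that costs almost nothing.

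**Conclusion.** The point holds as an inexpensive improvement to secondary analyses. APACHE II and baseline SOFA are named in no outcome model, and the free-day and SOFA ANCOVAs name only treatment arm, with age and sex to be considered.

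The 16% chance of an imbalance of at least 0.5 SD follows from the allocation alone. The shift of 0.10 to 0.25 SD and the rise in power from 80% to about 80–89% rest on an assumed correlation of 0.2 to 0.5, and the power gain is an upper bound. At a correlation of 0.2 there is essentially no gain. The case does not depend on any single value, because the covariate costs one degree of freedom and the data are already collected. For mortality, the only argument is for fewer parameters.

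**What to change.** In 9.4.3, before unblinding:

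- **SOFA:** name baseline SOFA as the covariate in the SOFA ANCOVA.
- **Ventilator-, ICU- and hospital-free days:** name APACHE II, taken over the pre-randomisation window of 8.1, as the covariate.
- **Mortality:** if severity is used, let it replace the named covariates instead of joining them. Treatment plus APACHE II, with smoking, age and sex moved to a sensitivity analysis, would be one way. APACHE II already contains age, and the general sentence on age and sex must be reconciled in the same edit.
- **Baseline window:** align the wording of 8.4 with 8.1, as a minor consistency edit.

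The cost is SAP wording and one degree of freedom in each ANCOVA. No new data are needed, and the mortality model would have fewer parameters.
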